## 2. Summary of Duration of Exposure to Vismodegib as a Monotherapy

Output ID: t\_ex\_dur\_bymon\_SE

Vismodegib Exposure	Safety Population (N=xxxx)	Person-Years
1 month or more	xxxx (xx.x%)	xxxx.xx
3 months or more	xxxx (xx.x%)	xxxx.xx
6 months or more	xxx (xx.x%)	xxx.xx
12 months or more	xxx (xx.x%)	xxx.xx
24 months or more	xx (x.x%)	xxx.xx
36 months or more	xx (x.x%)	xx.xx

Programming Note:

- N is number of Patients in the Safety Population.
- Vismodegib Exposure Duration categories derived as Total duration of Exposure in months which is calculated using (difference between first and last administration of Vismodegib) divided by 30.4375 (last dose date minus first dose date + 1)/30.4375.
- Patients with exposure of 1 month or more will be included in the summary frequencies (numerator). The denominator for percentages will be the subjects in the Safety Population.
- Person-years should be calculated as sum of exposure duration (in days) of patients in each category divided by 365.25.

3. Summary of Exposure to Vismodegib as a Monotherapy by Dose.  
Output ID: t\_ex\_bydose\_SE

Vismodegib Daily Exposure (mg)	Safety Population (N=xxxx)	Person-Years
150	xxxx (xxx.x%)	xxxx.xx

Programming Note:

- N is number of patients in the Safety population.
- Vismodegib Daily Exposure is the total daily dose taken by patient. This is constant at 150 mg as per protocol; no daily dose variations are permitted.
- Person-years should be calculated as sum of exposure duration in all patients in the safety population divided by 365.25.

4. Summary of Exposure to Vismodegib as a Monotherapy by Age Group and Gender

Output ID: t\_ex\_byage\_bysex\_SE

Age Group (Years)	Patients n (%)		Person-Years	
	Male (N=xxx)	Female (N=xxx)	Male (N=xxx)	Female (N=xxx)
<65	xxx (xx.x%)	xxx (xx.x%)	xxx.xx	xxx.xx
>=65	xxx (xx.x%)	xxx (xx.x%)	xxx.xx	xxx.xx
<75	xxx (xx.x%)	xxx (xx.x%)	xxx.xx	xxx.xx
>=75	xxx (xx.x%)	xxx (xx.x%)	xxx.xx	xxx.xx

Programming note:

- N is number of patients in each sex category (in the safety population).
- Age Groups derived on the basis of Baseline Age.
- Person-years should be calculated as sum of exposure duration of Patients for each category of gender and age group divided by 365.25.

## 5. Summary of Exposure to Vismodegib as a Monotherapy by Ethnicity

Output ID: t\_ex\_byrace\_SE

Race	Safety Population (N=xxxx)	Person-Years
n	xxxx	
WHITE	xxx (xx.x%)	xxx.xx
NOT APPLICABLE	xxx (xx.x%)	xxx.xx
OTHER	xx (x.x%)	xx.xx
BLACK OR AFRICAN AMERICAN	x (x.x%)	x.xx
ASIAN	x (x.x%)	x.xx

Programming note:

- N is number of patients in safety population.
- n is number of patients with non-missing race information.
- Race information comes from the Demography CRF page and as per SDTM controlled terminology "Black" should be mapped as "Black or African American".
- Race was recorded as "Not applicable" in France (hence the need for this category).
- Person-years should be calculated as sum of exposure duration of Patients in each race category divided by 365.25.

## 6. Summary of Exposure to Vismodegib as a Monotherapy by Gorlin Status

Output ID: t\_ex\_bygorlin\_SE

Disease Status		Safety Population (N=xxxx)	Person-Years
Locally Advanced	n	xxxx	
	Non-Gorlin Syndrome	xxx (xx.x%)	xxx.xx
	Gorlin Syndrome	xxx (xx.x%)	xxx.xx
Metastatic	n	xxxx	
	Non-Gorlin Syndrome	xxx (xx.x%)	xxx.xx
	Gorlin Syndrome	xxx (xx.x%)	xxx.xx

Programming note:

- N is number of patients in safety population.
- n is number of patients with non-missing Gorlin Syndrome information in each of disease status.
- *Gorlin Syndrome* information comes from "Gorlin Syndrome" CRF page.
- Person-years should be calculated as sum of exposure duration of patients in each Syndrome category and disease status category divided by 365.25.

### Programming note:

- *Cycle* and *Period Start Date* will be derived based on visit windowing algorithm.
- Information on *Reason for Treatment Break* and *Specify if Other* will come from the "Reason for breaks in treatment" CRF page.

## Adverse Events:

### General AE Reporting

Listings will include all AEs unless otherwise specified. A Treatment Emergent AE (TEAE) is defined as an AE that starts on or after the first day of study treatment and within 30 days of last dose (please see General Considerations for definition). Unless otherwise specified, AE and SAE summary tables will be restricted to TEAEs.

In STEVIE, the data collection guidelines require that the same AE is entered multiple times into the database, with a separate record for each change in toxicity grade or Lower Level Term. AEs can be reported using this or a “collapsed” Adverse Events analysis dataset.

The Collapsed Adverse Events dataset is derived by combining records that can be reasonably considered to be referring to a single AE term but with changes in toxicity grade (or lower level term). Records from the original AE dataset are grouped, and each group is represented in the collapsed dataset by a single record. The groups are built up by “chaining” records from the original dataset as follows:

- if the Subject ID, System Organ Class and Preferred Term are the same, and
- either the periods defined by the two AEs’ start and end dates overlap, or the Start Date of the later AE is  $\leq 2$  days after the End Date of the earlier one.

In the single record representing the “collapsed” AE:

- Subject ID, System Organ Class and Preferred Term are copied across from any of the records in the group (these are identical so it doesn’t matter which record these variables come from)
- Severity (i.e. toxicity grade) is taken as the most severe grade in the group
- Start Date is taken as the earliest start date in the group
- End Date, Lower Level Term and Outcome are taken from the record with the latest end date in the group

Examples are given on the next page.

Example of derivation of “collapsed” AEs:

Example 1:

SUBJID	System Organ Class	Preferred Term	Lower Level Term	Severity	Outcome	Start Date	End Date
	GASTROINTESTINAL DISORDERS	DYSPEPSI	DYSPEPSIA	GRADE 2 / MODERATE	RESOLVED		
	GASTROINTESTINAL DISORDERS	DYSPEPSI A	HEART BURN	GRADE 3 / SEVERE	RESOLVED		

Collapsed to:

	GASTROINTESTINAL DISORDERS	DYSPEPSI A	HEART BURN	GRADE 3 / SEVERE	RESOLVED		
--	----------------------------	------------	------------	------------------	----------	--	--

Example 2:

SUBJID	System Organ Class	Preferred Term	Lower Level Term	Severity	Outcome	Start Date	End Date
	MUSCULOSKELETAL	MUSCLE SPASMS	CRAMPS OF LOWER EXTREMITIES	GRADE 2 / MODERATE	RESOLVED		
	MUSCULOSKELETAL	MUSCLE SPASMS	CRAMP IN HAND	GRADE 2 / MODERATE	RESOLVED		
	MUSCULOSKELETAL	MUSCLE SPASMS	CRAMPS OF LOWER EXTREMITIES	GRADE 1 / MILD	RESOLVED		

Collapsed to:

	MUSCULOSKELETAL	MUSCLE SPASMS	CRAMP IN HAND	GRADE 2 / MODERATE	RESOLVED		
--	-----------------	---------------	---------------	--------------------	----------	--	--

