7.2 HANDLING OF SAFETY PARAMETERS

7.2.1 Recording and Collection of Adverse Events

Information about all AEs, whether volunteered by the patient, discovered by Investigator questioning, or detected through physical examination, laboratory test, or other means, will be collected on the Adverse Event eCRF page, documented in the patient's medical records, and followed as appropriate.

All AEs and SAEs, regardless of the relationship to the trial drug, will be recorded in the eCRF.

All AE reports should contain a brief description of the event, date and time of onset, date and time of resolution, intensity, treatment required, relationship to trial drug, action taken with the trial drug, outcome, and whether the AE is classified as serious.

All AEs experienced after the patient has started study treatment must be recorded on the AE form of the eCRF, as well as all new AEs experienced during the study and during further five Safety Follow-Up Visits 1 month, 3 months, 6 months, 9 months, and 12 months after the last dose of study treatment (± 5 days). SAEs considered related to study drug are to be reported indefinitely.

A pre-existing medical condition that is present at the start of the study should be recorded on the Medical History eCRF.

Worsening and/or progression of advanced BCC should not be recorded as an AE or SAE. These data will be captured as efficacy assessment data only.

If a female patient becomes pregnant while receiving investigational therapy or within 9 months *or within the designated window per approved local prescribing information for vismodegib (where available), whichever is longer*, after the last dose of investigational product, the Investigator should report to the Sponsor immediately within one working day (24 hours) of learning of the pregnancy.

Abortion, whether therapeutic or spontaneous, should always be classified as serious (as the Sponsor considers these medically significant), recorded on the eCRF, and expeditiously reported to the Sponsor.

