7.2.2 Reporting of Serious Adverse Events (Immediately Reportable)

Any clinical AE or abnormal laboratory test value that is *serious* and which occurs during the course of the study (as defined in Section 7.1.1.3 above), must be reported to Roche **within 24 hours** of the Investigator becoming aware of the event (expedited reporting).

The following proviso applies:

- **During the Screening Period, after written informed consent has been signed only SAEs related to protocol procedures will be reported.**
- **From the first administration of vismodegib, all SAEs must be reported.**

Related SAEs **MUST** be collected and reported regardless of the time elapsed from the last study drug administration, even if the study has been closed. Suspected Unexpected Serious Adverse Reactions (SUSARs) are reported to Investigators at each site and associated Institutional Review Board/Independent Ethics Committee (IRB/IEC) when the following conditions occur:

- The event must be a SAE
- There must be a certain degree of probability that the event is an adverse reaction from the administered drug
- The adverse reaction must be unexpected, that is to say, not foreseen in the Investigator's Brochure (for an unauthorized medicinal product)

When all patients at a particular site are off treatment as defined by the protocol:

- Only individual SUSAR reports originating in that particular trial will be forwarded to the site and associated IRB/IEC on an expedited basis
- Individual SUSARs considered to be a significant safety issue and/or which result in Roche recommending a change to the ICF, will be reported in an expedited manner to all Investigators and IRBs/IECs
- SUSAR reports originating from other trials using the same IMP will be provided as 6-monthly SUSAR Reports to Investigators and IRBs/IECs where long-term follow-up studies are carried out, unless they are considered significant

Unrelated SAEs must be collected and reported during the study and for up to 12 months after the last dose of study medication.

This study adheres to the definition and reporting requirements of **ICH Guideline for Clinical Safety Data Management, Definitions and Standards for Expedited Reporting, Topic E2**. Complete information can be found in [Appendix 4](#).

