8.1.1 Primary Variables

The primary objective of this trial is to assess the safety of vismodegib in patients with locally advanced or metastatic BCC.

Consequently, the following safety variables are primary variables: all AEs, AEs Grade 3 or 4, AEs leading to drug interruptions or discontinuations, SAEs, cause of death on study, premature discontinuation from study and treatment, laboratory parameters (hematology and serum chemistry), and exposure to study medication.

Continuous data will be summarized using mean, standard deviation, median, minimum, and maximum. Discrete data will be summarized using frequencies and percentages. No adjustments for multiplicity of endpoints or within-subgroup comparisons will be used in the analyses.

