8.2.2 Safety Analysis

The safety variables will be summarized for the safety population, where the safety population will include all patients who received at least one dose of study medication.

If the safety population differs by less than 5 patients from the ITT population, then all summaries will be presented only for the safety population.

AEs, AE Grade 3 or 4, AEs leading to drug interruptions or discontinuation and SAEs

All AEs will be assessed according to the NCI-CTCAE, v4.0 grading system.

The analysis of AEs will focus on treatment-emergent AEs, i.e., AEs occurring on or after the first day of vismodegib administration. Non-treatment-emergent AEs (i.e., those occurring before commencement of study medication) will only be listed.

The incidence, type, and severity of AEs will be summarized according to the primary system organ class (SOC) and within each SOC by the Medical Dictionary for Regulatory Activities (MedDRA) preferred term. Summary tables might be presented for time to first onset of the AE of special interest.

SAEs and AEs leading to drug interruptions or discontinuation will be analyzed similarly. Cause of death will also be summarized and listed.

Premature withdrawal from study and treatment

The number of patients who prematurely discontinued treatment, along with the corresponding reason(s) for discontinuation, will be summarized and listed. The discontinuation from study will be also summarized and listed.

Exposure to Study Medication

The exposure of vismodegib will be summarized by means of descriptive statistics for the cumulative dose and frequency tables (percentages) by Cycles and/or Weeks of treatment. The reason for the dose discontinuation other than disease progression will be also summarized.

Laboratory parameters

Laboratory parameters, hematology, and serum chemistry will be presented in shift tables of NCI-CTCAE grade at baseline versus worst grade during the treatment period. Summary of laboratory parameters will be presented by means, standard deviation, minimum, and maximum. Graphical presentations of the mean value of selected laboratory parameters might be also displayed.

Physical Examination

Physical examination variables will be summarized over time by visit and reported in patient listings.

Vital Signs and ECG

Vital signs and ECG will be summarized over time by means of mean, median, and range (mean and maximum), and will be presented graphically over time.

ECOG PS

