AET02	
Output ID: t_ae2_*
 
 
● Analysis Populations: Enrolled Population Output will be repeated for different population combinations - please see the LoPO for details of these combinations
   
● Column Variables: Disease Status (Locally Advanced, Metastatic)
   
● Column Totals: Totals of non-missing Disease Status
   
● Analysis Variables: MedDRA System Organ Class, MedDRA Preferred Term.
   
● Statistics and Calculation Methods: Use proq freq for events or proc sql for patient counts.
   
● Numeric Precision and Formatting of Statistics: Use standard display in the mockup
   
● Optional Subsetting: For each System Organ Class and Preferred Term, include Total number of patients with at least one AE, Overall total number of events
 

Programming Notes:

- Table to be repeated for TEAEs leading to Death, Serious TEAEs, TEAEs of Grades 3 to 5 and TEAEs Leading to Study Drug Discontinuation.

- Rate of AEs per 100 Patient Years by Exposure Duration:

STREAM Template	Description
AET02	
Output ID: t_ae_byptyr_*
 
 
• Analysis Populations: Safety Output will be repeated for different population combinations - please see the LoPO for details of these combinations
 
• Column Variables: Exposure Duration Categories (< 12 Months Exposure, >= 12 Months Exposure)
 
• Column Totals: None
 
• Analysis Variables: MedDRA System Organ Class, MedDRA Preferred Term.
 
• Numeric Precision and Formatting of Statistics: Use standard display in the mockup
 
• Optional Subsetting: For each System Organ Class and Preferred Term, include Total number of patients with at least one AE, Overall total number of events
 

Disposition of patients with an AE ongoing at treatment discontinuation:

STREAM Template	Description

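### The SAP ends the treatment-emergent window 30 days after last dose, the protocol sets no end, and no specified AE or SAE incidence table covers later new onsets

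*SAP*

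**What the plan says.** **SAP.** Under General AE Reporting, a treatment-emergent AE (TEAE) is one that "starts on or after the first day of study treatment and within 30 days of last dose". The same paragraph sets the default: "Unless otherwise specified, AE and SAE summary tables will be restricted to TEAEs". Listings, by contrast, take all AEs. For the Enrolled-population output (t_ae2) the programming note reads "Table to be repeated for TEAEs leading to Death, Serious TEAEs, TEAEs of Grades 3 to 5", and adds TEAEs that led to stopping study drug.

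**Protocol, definition.** Section 8.2.2 puts the focus on treatment-emergent AEs, which it explains as "AEs occurring on or after the first day of vismodegib administration". Of the non-treatment-emergent ones it says: "those occurring before commencement of study medication) will only be listed". The Synopsis and Section 5.3.7 define the term in the same way. None of the three gives an end date.

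**Protocol, collection and role.** Section 7.2.1 requires recording of "all new AEs experienced during the study and during further five Safety Follow-Up Visits", which fall at 1, 3, 6, 9 and 12 months after last dose. Section 7.2.2 states: "Unrelated SAEs must be collected and reported during the study and for up to 12 months after the last dose of study medication". Related SAEs have no time limit. Section 8.1.1 says that "the following safety variables are primary variables: all AEs, AEs Grade 3 or 4, AEs leading to drug interruptions or discontinuations, SAEs", and names further safety variables.

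**Follow-up length.** The SAP (Disposition; Potentially Reversible AE Population) gives patients under protocol versions 1 and 2 one month of follow-up, and patients under version 3 or later 12 months.

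**The concern.** Safety is the primary objective, and AEs and SAEs are primary variables. The two documents use one term for two different sets of events, so the incidence that the SAP reports as treatment-emergent is not the quantity the protocol defines under that name.

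The difference falls on events that first appear after day 30. Take an SAE that starts four months after the last dose in a patient followed for 12 months. Under the protocol it is treatment-emergent and belongs in the summaries. Under the SAP it is not a TEAE and enters no specified incidence table. A reader of the tables would have no incidence of such events by system organ class, preferred term, seriousness or grade, although the sites were asked to collect them.

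**Working it through.** The check has two steps: compare the definitions, then read each AE output in the SAP for an exception to the default.

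**Step 1, definitions.**
- Protocol 8.2.2: onset on or after first dose, with no end. Listing-only applies to pre-dose events.
- SAP: onset from first treatment day to 30 days after last dose.
- The protocol refers details to the SAP for the interim analyses (8.2.1.2) and for quality of life and symptoms (8.2.3.2). It does not do so for the AE definition in 8.2.2.

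**Step 2, outputs in the SAP's Adverse Events section.**
- Overall summary (t_ae_o); AEs by class and term (t_ae); by subgroup, severity, drug relationship, exposure duration, outcome and age group; resolution of collapsed AEs (t_ae_out_c); rate per 100 patient-years (t_ae_byptyr). None states an onset window, so all take the TEAE default.
- Enrolled-population table (t_ae2) and its repeats for fatal, serious, Grade 3 to 5 and drug-discontinuation events. These are TEAE by name.
- AEs still ongoing at last assessment (t_ae_out_ongo outputs) and disposition of patients with an ongoing AE (t_ae_ds_persae). These cover only AEs already present when treatment stopped, so they contain no new onsets.
- Listing of All Adverse Events. It includes late onsets.
- Total deaths and withdrawals from study due to an AE (t_ae_o), Patient Disposition, and Summary of Deaths. These can count a late event that is fatal or ends participation, but only as a total.

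No specified AE or SAE incidence table therefore covers new onsets from day 31 to month 12.

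**Reach in calendar time.** A full 12-month follow-up has 365 − 30 = 335 days after the window, and 335/365 = 91.8%. Four of the five safety visits (months 3, 6, 9 and 12) lie beyond day 30. The month-1 visit, with its ±5 days, straddles the limit. This measures time, not events.

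**Size in events.** The documents give no count of AEs by onset after day 30, so the effect on any incidence cannot be calculated. The protocol's own incidence precision reproduces (Table 3: 120 of 1200 gives an exact interval of 8.36% to 11.84%, printed as 8.4% to 11.8%), but the point does not depend on it.

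**The case against.** The best defence is that 30 days is a sensible common window. Patients under versions 1 and 2 were followed for one month only, so an open-ended definition would mix unequal ascertainment in one denominator. The SAP also uses a 30-day limit for CPK, vital signs, Skindex-16 and MDASI. Protocol 7.1.6 stops following unrelated Grade 1 or 2 AEs at 30 days. All of this stands as a reason to keep the 30-day tables. It does not remove the mismatch. Section 7.1.6 concerns how long existing events are followed; it neither limits the recording of new events in 7.2.1 nor redefines the term.

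A second defence is that the reason, or a further table, may sit in material not seen. The SAP places definitions in DAP M3. It also uses the LoPO, in the AE section for population combinations and in the MDASI section for analysis criteria. This stands as a limit: the claim is about the text available.

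A reader might also infer three stronger things, which the documents do not support.
- *Late events are lost or hidden.* They are listed in full, and deaths are tabulated.
- *Day 30 is too early because drug is still present.* The 12-day half-life in Protocol 1.1.2.1.1 follows a single dose. The same section puts steady state at about 7 days of daily dosing. A linear 12-day half-life would reach only 1 − 0.5^(7/12) = 33% of steady state by then, and 1.1.2.1.6 describes nonlinear kinetics. The 10 to 14 days in Section 6.1 are preliminary findings in healthy subjects. No half-life count for the period after continuous dosing can rest on these figures.
- *A stated share of patients is affected.* The only population sizes are in mock-ups of uncertain data cut. Two CPK mock-ups for the same described population show 514 patients and 120 + 62 = 182 patients with a value. One AE mock-up refers to November 2013 and the death summary to March 2015.

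**Conclusion.** The point holds as a conflict of definitions with a limited practical consequence. The SAP narrows a term that the protocol leaves open at the end, and new AEs and SAEs from day 31 to month 12 are then listed but not tabulated by class, term, seriousness or grade. It is minor: no data are lost, the tables that exist remain useful, and the number of late-onset events is unknown.

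The conclusion rests on two assumptions: that the LoPO and DAP M3 add no late-onset table, and that the TEAE default applies wherever an AE table states no window. It concerns only patients followed beyond one month. On who those patients are, the SAP has two rules. The Disposition text goes by the version under which a patient enrolled, and the programming note to Patient Disposition goes by the latest version consented to. The two differ for patients who enrolled under version 1 or 2 and later re-consented.

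**What to change.** 1. Reconcile the SAP definition with Protocol 8.2.2 and state the reason for the 30-day limit.
2. Keep the 30-day tables and label them as on-treatment plus 30 days.
3. Add one descriptive table of AEs, SAEs, Grade 3 to 5 AEs and fatal AEs with onset from day 31 after last dose to the end of safety follow-up. Use PV3PLUS patients who stopped treatment and were still followed after day 30. Give the number at risk, the number with at least one event, and the rate per 100 person-years from day 31 to first event, death, end of follow-up or data cut. Class and term rows can be limited to patient counts, which avoids a separate person-time for every term. Flag events that start after commercial vismodegib or new anti-cancer therapy; both are already collected.
4. State which rule, version at enrolment or latest version consented to, sets 12-month follow-up.

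The SAP already reports CPK in two windows side by side, so the layout has a precedent. The cost is wording, one more table, and a new derivation of follow-up person-time, because the SAP's person-years are exposure time. Late events will be confounded by later therapy. Protocol 5.3.4 leaves open how far observation continues once new anti-cancer therapy starts, so the table must say how that time is handled. Patients with one month of follow-up do not enter it. Items 1 and 2 alone remove the contradiction; item 3 fills the reporting gap.
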